8 STUDY ASSESSMENTS AND PROCEDURES

8.1 EFFICACY ASSESSMENTS

Cognitive Testing:

Participants who are enrolled in this study will undergo a standardized neuropsychological test battery at 3 time points with the test score calculated at 12-month follow-up is considered the primary endpoint for the trial:

- (1) Baseline: prior to procedure.
- (2) Early Post-op: At 6 months post-discharge from hospital, to investigate short-term cognitive outcome;
- (3) Late Post-op: At 12 months post-discharge from hospital, to investigate long-term cognitive outcome.

We selected a battery of tests that includes a standard screening measure (the MoCA), to facilitate comparisons to other studies that have used this as the primary cognitive outcome measure. The battery includes a number of well-standardized, widely used cognitive tests that measure various aspects of cognitive and behavioral functioning, including intelligence, attention, processing speed, memory, speech and language, visuoconstruction, and executive functioning. We selected a set of tests that can be administered in a one-hour session, and that are highly efficient (providing the highest yield for time required). Also, for all of these tests we have standardized information about the effects of

repeat assessment, and/or multiple forms of the tests that allow practice effects to be either obviated or measured and factored into the analyses. A general reference for the neuropsychological assessment battery we are proposing is Lezak, Howieson, Bigler, and [name] (2012)⁵³, the standard textbook on neuropsychological assessment on which one of the current co-investigators ([name]) is a co-author.

The test battery at each time point will include the following measures:

1. Montreal Cognitive Assessment (MoCA): This is a widely used screening instrument designed for the detection of cognitive impairment ⁶². Total points possible on this test range from 0 – 30.
2. Wide Range Achievement Test-5 (WRAT-5)¹⁰⁴, Word Reading subtest: This is a single-word oral reading test, well-validated as an estimate of baseline general intelligence (Wilkinson & Robertson, 2017). The number of correctly read words is converted to an age-adjusted standard score (mean = 100, standard deviation = 15).
3. Wechsler Adult Intelligence Scale – IV (WAIS-IV), Digit Span subtest: This test measures complex attention and working memory. The participant is asked to repeat a series of aurally presented digits of increasing length (a) verbatim, (b) in reverse order, and then (c) sequentially from lowest to highest ¹⁰². The total score is converted to an age-corrected scaled score (mean = 10, standard deviation = 3).
4. WAIS-IV, Coding subtest: This test measures sustained attention and processing speed. Using a key, the participant writes the symbol corresponding to its number as quickly and accurately as possible. The total score is converted to an age-corrected scaled score (mean = 10, standard deviation = 3).
5. WAIS-IV, Matrix Reasoning subtest: This test measures concept formation and abstract reasoning. The participant selects one of five options to complete a visual pattern. The total score is converted to an age-corrected scaled score (mean = 10, standard deviation = 3).
6. Hopkins Verbal Learning Test – Revised (HVLT-R): This is a test of learning and memory. The participant is read a list of 12 semantically categorized words (four words in each of three categories) and asked to recall as many as possible. The test consists of three learning trials, followed by delayed recall and yes/no recognition trials ¹³. The scores from this test are (a) sum of the total correct responses for the learning trials, (b) the number recalled at the delay, and (c) the recognition discrimination index (number of correctly recognized – number of false positives). Scores are converted to T-scores.
7. Benton Visual Retention Test (BVRT) ⁷: This test measures attention, working memory, and visual perceptual-constructional skills. The participant is shown a page containing one to three geometric designs for 10 seconds, and then is instructed to draw the design(s) immediately after the stimulus is removed ⁸⁸. Scores are the total number of correct designs (range 0 – 10) and total number of errors, converted to z-scores.
8. Controlled Oral Word Association (COWA) Test: This test measures flexible thinking and verbal fluency. The participant is asked to orally generate as many words as possible in 60 seconds, for each of three letters ⁷. The score (age- and gender-corrected) is the total number of words generated across the three trials; this is converted to a percentile score.
9. Boston Naming Test (BNT): This is a test of confrontation naming in which the participant is presented line-drawn pictures and asked to name them ⁴⁷. The overall test contains 60 items, from which three equivalent short-form versions (20 items each) will be used in the current study ⁵. The score is the number of correctly named items (range 0 – 20), converted to a z-score.
10. Boston Diagnostic Aphasia Examination, Complex Ideational Material subtest (CIM): This is an auditory comprehension test developed to measure sustained attention and receptive language skills. It consists of yes/no questions of increasing difficulty in which the participant must recall common facts, and infer details contained in short, aurally presented stories ³⁸. The range of scores on this test is 0 – 12, and raw scores are converted to T-scores.

11. Trail-Making Test, part A (TMT-A): This test measures attention, processing speed, and visuomotor skills. Participants are asked to connect 25 numbered circles as quickly and accurately as possible 78. The score is the time to completion (in seconds), converted to a T-score.
12. Trail-Making Test, part B (TMT-B): This test measures divided attention, processing speed, cognitive flexibility, and executive function. The participant is asked to connect 25 numbered and lettered circles, alternating between the two in numerical and alphabetical order (e.g., 1, A, 2, B, 3, C, etc.). The score is the time to completion (in seconds), converted to a T-score.
13. Beck Depression Inventory-Fast Screen (BDI-FS): This is a self-report inventory of depressive symptomatology, designed for use in persons with medical illnesses⁶. Scores are converted to a range of depression severity (none, mild, moderate, severe).
14. Iowa Scales of Personality Change (ISPC): On this measure, a collateral of the patient (e.g., spouse, child) rates behavioral and personality characteristics of the patient before and after a particular event (for the current study, this will be the surgical intervention) 4. The ISPC measures changes in personality and behavior, and will be administered only at the post-surgery evaluations (to the collateral). Scores are converted to z-scores.

The score on the MoCA will serve as an overall proxy for cognitive outcome, and can be used to measure change (e.g., pre to post). Scores from tests 2-12 in the proposed neuropsychological battery will be converted to z-scores, to facilitate direct comparisons across the test battery for pre to post (including short- and long-term outcomes). These will also be used to analyze changes in specific cognitive domains. The score from the BDI-FS will be used as a covariate to assess the role of depressive symptomatology in cognitive performance.

MR Image Acquisition MR imaging will be performed on a GE 750W 3T scanner using a 32-channel head coil. Anatomical images will include volumetric T1 MPRAGE (TI=900ms, TE=3ms, TR=3000ms, flip angle=10°, FOV=210x210x210mm, matrix=420x420x420, bandwidth= 244Hz/pixel, acceleration=4) and T2 CUBE (TE= 90ms, TR= 3000ms, echo train length=130, FOV=210x210x210mm, matrix=420x420x420, bandwidth= 488Hz/pixel, acceleration=4) sagittal scans with a 0.5 mm isotropic spatial resolution. The 1H MRS data will be acquired from voxels placed in the centrum semiovale in the ipsilateral side of COICA using a single-voxel semi-LASER sequence with the following parameters: TE=288, TR=4000ms, Voxel size = 20x20x20mm, Spectral Width=5000Hz, Vector size=4096, and NEX=32. Data will be collected with and without water suppression.

Volumetric Anatomical Image Analysis: The volumetric anatomical T1- and T2-weighted images will be analyzed using BRAINS AutoWorkup 72 that includes a FreeSurfer 22,32,33 module using Nipype 39. The default FreeSurfer pipeline will be updated to segment the brain and generate the cortical surface using a 0.5mm resolution for the reconstruction. The original images and the automated pipeline results will be checked for validity by a trained technician who is blind to subject status. Of primary interest for this analysis is the volume of the hippocampus and amygdala as generated by this pipeline

MRI-Spectroscopy (MRS) Analysis. The 1H MRS data will be analyzed using LCModel 77. The water suppressed and non-water suppressed data will be analyzed to generate absolute concentrations after performing phase and eddy current correction. We will obtain concentrations measurements for NAA, glutamate+glutamine (Glx), total creatine (Cr+PCr), total choline (tCho), and lactate from the 1H data. Only metabolites with a Cramer-Rao lower bound of less than 20% will be included in further analyses. Lactate concentrations will be the primary metabolite of interest for this study

All MRI images required by the protocol may be completed under sedative, if subject requests and PI deems them eligible.

8.2 SAFETY AND OTHER ASSESSMENTS

Stopping rules or safety triggers for the study:

The occurrence of the following potential side effects and risks associated with procedure will trigger prompt reporting and review by the DSMB to discuss the events and decide on the continuation of the trial. The following adverse events, will be reported to the DSMB: 1) Any intracranial hemorrhage within 72 hours post procedure, 2) Any stroke within 30 days post procedure; 3) Any seizure within 72 hours post procedure; and 4) any injury to cervical ICA during the procedure.

Based on complication rates in the trial to date (June 2021), the occurrence of one additional event in these categories will trigger a suspension of enrollment in the trial and meeting of the DSMB to discuss the events and decide on the continuation of the trial

The cumulative rates will also be assessed at different time points: A) after completed enrollment of the first 10 subjects, B) completed enrollment of first 20 subjects, & C) Completed enrollment of first 30 subjects. A rate of > 20% will lead to automatic stop and evaluation by the DSMB.

Safety oversight for this study will be provided by both the DSMB and an independent Medical Safety Monitor ([name]).

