2.3 RISK/BENEFIT ASSESSMENT

2.3.1 KNOWN POTENTIAL RISKS

Risks include:

1. Ischemic stroke
2. hemorrhagic stroke

3. Seizure
4. Carotid cavernous fistula
5. Visual acuity deficits.
6. Extravasation of contrast secondary to injury to cervical ICA during the procedure; and
7. Contrast allergy
8. Radiation exposure from CTP and x-rays associated with diagnostic angiograms and intervention.
9. renal dysfunction

Additional risks:

There is a very minimal risk of violation of confidentiality as some patient identifiers will be collected as part of the data collection process. Emotional or psychological risk could ensue if this were to occur. No financial, legal, social or physical risks are anticipated.

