2.3.3 ASSESSMENT OF POTENTIAL RISKS AND BENEFITS

The research team have devised a classification system that helps select subjects that are suitable for the procedure and minimize the risks associated with intervention. The research team will use that classification to enroll subjects. This classification was tested in pilot study among 4 institutions and was very effective.

The study is designed to reduce the risks by careful pre-screening, monitoring and follow up visits. To reduce the risk of loss of confidentiality, precautions will be taken to ensure privacy. The investigators and the study team will maintain appropriate medical and research records for the study, in compliance with ICH E6 GCP, section 4.9 and regulatory and institutional requirements for the protection of confidentiality of subjects. Research records generated in this study will be stored in a file cabinet in a locked room and/or on a secure electronic database. Only the authorized study team will have access to the data. Research team members have separate usernames and passwords. Imaging collected during the study will be identified by a subject number, IRB protocol number, and date of collection. All personal data will be de-identified and kept separately from patients' identifiers. A subject will be assigned a research study ID and all research data will be identified with this research study ID. Whenever possible, all personal information will be blacked out on all hard copy records and replaced with research study ID; if research team writes an article or report about the study or share the data with others, all personal information that can identify a subject will be removed.

Data and Safety Monitoring Board [DSMB]:

The DSMB will be appointed by the NIA to monitor the performance of the study. The Steering Committee will prepare regular reports summarizing patient accrual and the morbidity and mortality experienced in the study. The DSMB will also review the cumulative outcome data at regular intervals (every 6 months).

During hospitalization and for the intervention arm, [name] will monitor for adverse events. He will check on the subjects post op and every day while in hospital.

Definitions:

Stroke: any new ischemic changes found either on head CT and/or MRI of the brain and associated with new neurological deficits that were not present prior to intervention.

TIA: any new neurological deficits resolved within 24 hours of symptom onset.

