The occurrence of following potential side effects and risks associated with procedure will trigger a prompt reporting and review by the DSMB to discuss the events and decide on the continuation of the trial. The following adverse events will be reported to the DSMB: 1) Any intracranial hemorrhage within 72 hours post procedure, 2) Any stroke within 30 days post procedure; 3) Any seizure within 72 hours post procedure; and 4) Any injury to cervical ICA during the procedure.

Based on complication rates in the trial to date (June 2021), the occurrence of one additional event in these categories will trigger a suspension of enrollment in the trial and meeting of the DSMB to discuss the events and decide on the continuation of the trial

A combined rate of > 20% of the above adverse events at any time during the study will lead evaluation by the DSMB. The cumulative rate of these events will also be assessed at different time points: A) after completed enrolment of the first 10 subjects, B) completed enrollment of first 20 subjects, and C) Completed enrollment of first 30 subjects. If any of these thresholds are crossed, the study will automatically be placed on hold until the investigators and the DSMB can conduct a review of events. All adverse events (AEs) will be collected, recorded, and analyzed. Safety oversight for this study will be provided by both the DSMB and an independent Medical Safety Monitor ([name]).

Adverse Event (AE) Reporting:

Any potential adverse event or a serious adverse event mentioned above will be reported during the trial. An AE will be defined as any unfavorable and/or unintended sign, symptom, or injury temporally associated with the procedure or other study medication. A serious adverse event (SAE) is defined as any untoward/undesirable adverse experience related to a study intervention/medication that results in any of the following outcomes: 1) death; 2) a life-threatening adverse experience; 3) need for additional surgery; 4) a permanent or significant disability/incapacity; 5) important medical events that may not result in death, be life-threatening, or require additional surgery.

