3 OBJECTIVES AND ENDPOINTS

OBJECTIVES	ENDPOINTS	JUSTIFICATION FOR ENDPOINTS
Primary		
Endovascular revascularization that improves cognitive outcome	Cognitive outcome at 12-month follow-up assessed mainly by a specifically designed battery of 14 cognitive tests including the MoCA.	The battery of 14 tests including MoCA are designed to test tight hemisphere domain, left hemisphere domain, and global domain to assess for cognitive improvement
Secondary		
To test the safety of the procedure	1. Safety: Occurrence of Stroke, Cerebral Hemorrhage, or Death	1. These are the expected adverse events from this procedure and hence will be used to monitor safety
Tertiary/Exploratory		
To test the hypothesis that subjects with symptomatic COICAs and mild/moderate cognitive dysfunction have associated, measurable biomarkers	1. Biomarkers: A) The presence/absence of lactate on 1H-MRI spectroscopy in centrum semiovale in the ipsilateral side of COICA; B) The change in size of amygdala and hippocampus in the ipsilateral side of COICA; C) Resolution/improvement of increased MTT and/or PTT (normalization of MTT and/or PTT) on CTP. 2. Gender difference.	These are objective biomarkers of improved cerebral perfusion and improved cognitive outcome.

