8.3.2 DEFINITION OF SERIOUS ADVERSE EVENTS (SAE)

Adverse Event (AE) Reporting:

Any potential adverse event or a serious adverse event mentioned above will be reported during the trial. An AE will be defined as any unfavorable and/or unintended sign, symptom, or injury temporally associated with the procedure or other study medication. A serious adverse event (SAE) is defined as any untoward/undesirable adverse experience related to a study intervention/medication that results in any of the following outcomes: 1) death; 2) a life-threatening adverse experience; 3) need for additional surgery; 4) a permanent or significant disability/incapacity; 5) important medical events that may not result in death, be life-threatening, or require additional surgery.

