9.4.3 ANALYSIS OF THE SECONDARY ENDPOINT(S)

The safety measures of occurrence of Stroke/TIA, cerebral hemorrhage, or death will be analyzed as frequency within the 30-day post-procedure period. Analysis will be done in aggregate of the events combined and individually using a Kaplan-Meier survival estimation with a Logrank test. Adjustment for age, etiology of ischemia, and side of occlusion will be done using a Cox Model Regression. A two-sided type I error rate of 0.05 will be used.

Analysis of the Tertiary/exploratory Endpoint

Tertiary/exploratory endpoints will be analyzed individually. The presence/absence of lactate will be estimated by a proportion and evaluated using a Fisher's Exact Test. The change in sizes of amygdala and hippocampus in the ipsilateral side of COICA will be using a T-Test of the difference. Improved and/or normalization of MTT and/or PTT on CTP specifically in the ipsilateral MCA territory will be analyzed using a T-Test.

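### The event list that suspends enrollment omits death, and is unclear about intracranial hemorrhage after 72 hours

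*Combined protocol and SAP*

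**What the plan says.** The same four-item list stands in sections 2.3.3, 8.2 and 8.3.5. Items one and two are "1) Any intracranial hemorrhage within 72 hours post procedure, 2) Any stroke within 30 days post procedure". The third is seizure in the first 72 hours, and the fourth is damage to the cervical ICA while the procedure is under way. All three sections add that, given the complications seen up to June 2021, "the occurrence of one additional event in these categories will trigger a suspension of enrollment in the trial". Sections 2.3.3 and 8.2 also carry a cumulative rule. In 2.3.3 it is worded as "A combined rate of > 20% of the above adverse events at any time during the study", and both sections attach an automatic stop or hold to crossing it.

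The safety endpoint is built differently. Section 3 names stroke, cerebral hemorrhage and death, and justifies them so: "These are the expected adverse events from this procedure and hence will be used to monitor safety". Section 9.4.3 sets the window: "The safety measures of occurrence of Stroke/TIA, cerebral hemorrhage, or death will be analyzed as frequency within the 30-day post-procedure period".

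On the meaning of stroke, the definitions in 2.3.3 read "Stroke: any new ischemic changes found either on head CT and/or MRI of the brain", with new neurological deficits also required. The risk lists in 2.3.1 and 2.3.3 enter ischemic stroke and, as a separate item, "hemorrhagic stroke".

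**The concern.** Both automatic rules act only on listed categories, so the list decides what pauses the trial. Deaths that follow a listed event are caught through that event. A death without one is not: a cardiac death, an access-site death, or a fatal reaction to contrast (contrast allergy is a named risk in 2.3.1 but not a trigger). The gravest component of the safety endpoint then has a weaker automatic response than a seizure, which is not in the endpoint at all.

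The second gap is smaller. Item 1 stops at 72 hours. Whether a symptomatic bleed after that, up to day 30, falls under item 2 depends on which usage of stroke applies. The exposure does not end at 72 hours: under 4.1, patients without signs of hemorrhage are loaded with clopidogrel and aspirin at 24 hours and stay on both for 12 months. On the ischemic-only reading, even a fatal bleed on day 10 would meet no item on the list.

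**Working it through.** The point rests on the text, so the first two steps set the sections side by side. The third puts a ceiling on the consequence.

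**Step 1. What each rule does with each event.**

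| Event after the procedure | Suspends enrollment (2.3.3, 8.2, 8.3.5) | Counts in the 20% rate (2.3.3, 8.2) | In the 30-day endpoint (9.4.3) |
|---|---|---|---|
| Seizure at 48 hours | Yes | Yes | No |
| Intracranial hemorrhage at 48 hours | Yes | Yes | Yes |
| Ischemic stroke on day 10 | Yes | Yes | Yes |
| Symptomatic intracranial hemorrhage on day 10 | Only if stroke includes hemorrhage | Only if stroke includes hemorrhage | Yes |
| Death without a listed event | No | No | Yes |

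The fourth row concerns bleeds found clinically. The schedule in 1.3 has no brain imaging between day 4 and day 30, so nothing is claimed about silent ones.

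**Step 2. Does any other section hold enrollment after a death?**

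- 2.3.3, adverse event reporting: events during surgery go to the coordinator and the Medical Safety Monitor within 3 hours, and on to the DSMB, NIH and/or IRB within 24 hours or as soon as feasible. No hold is attached.
- 8.3.6: adverse events go to the medical monitor as they happen, and serious ones to the DSMB and IRB as required. No hold is attached.
- 8.3.2: an adverse event is defined by timing, not relatedness. A serious one is an "adverse experience related to a study intervention/medication that results in any of the following outcomes: 1) death" or another listed outcome. A death judged unrelated is therefore not a serious adverse event under this wording, although the event behind it would still go to the monitor.
- 8.4.1 and 8.4.2: an unforeseen device-associated death is an unanticipated problem and goes to the DSMB and IRB. Suspending enrollment appears only as an example of what might be considered.
- 4.4: early termination is tied to the four trigger categories plus death. The adjacent line defines successful completion as the one-year cognitive assessment, which suggests individual participants. A trial-level reading is possible. Neither reading states an enrollment hold.
- 9.4.6 and 10.1.6: scheduled review is every 6 months or every 10 patients.

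Reporting routes exist for death; an automatic suspension does not.

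**Step 3. Worst-case ceiling.** Inputs: 1 subject per 5 weeks planned, and 1 per 10 weeks as the futility rate (10.1.2); a 6-month review interval, taken as 26 weeks (10.1.6); 1:1 allocation (4.1); 19 surgical subjects planned (9.2).

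- Planned accrual: 26 / 5 = 5.2 enrolled; 5.2 / 2 = 2.6 to surgery; 2.6 / 19 = 13.7% of the surgical arm.
- Event midway through the interval: 13 / 5 = 2.6 enrolled; 1.3 to surgery.
- Futility-rate accrual, full interval: 26 / 10 = 2.6 enrolled; 1.3 to surgery.
- The 10-patient review takes 10 × 5 = 50 weeks at planned accrual, so the 6-month review normally comes first.

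These figures apply only if no report leads the DSMB to act sooner. They also treat all accrual as randomized; any subjects entering the third arm would lower the surgical numbers.

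**The case against.** The strongest reply is that the trial does not depend on the trigger list to learn of a death. A death during surgery reaches the DSMB, NIH and/or IRB within about a day. An event close in time to the procedure goes to an independent monitor as it happens, whatever its judged cause. An unforeseen device-associated death goes to the DSMB and IRB. This stands. A reader might infer that the board could stay unaware of a death until its next scheduled review. The documents do not support that as the usual course: it needs a death outside surgery, judged unrelated, not device-associated, and not passed on by the monitor. The ceiling in Step 3 belongs to that residual case.

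A second reply is that the amendment history (10.3) ties the adjusted stopping rules to a DSMB ruling, so the board may have chosen this list. The ruling is not in the documents, and nothing shows that death was either considered or excluded. That is a reason to make the change with the board's agreement, not a reason to leave the list alone.

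Third, 4.4 may show that the authors already group death with the triggers. If so, the three lists do not carry that intention through.

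Fourth, the risk lists already treat hemorrhage as a kind of stroke, so item 2 can be read to cover a late symptomatic bleed. That is fair, and it is why this half is an ambiguity and not a definite omission.

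Finally, in the pilot of 31 subjects (2.2) no complication led to death. That is relevant context, but too small a series to show that death is rare.

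**Conclusion.** The concern holds as a gap in the automatic response. A post-procedure death without a listed event does not suspend enrollment and is not counted in the 20% rate, although the plan makes death a 30-day safety outcome. A symptomatic intracranial hemorrhage after 72 hours is a smaller, definitional uncertainty.

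No frequency can be given, because the documents have no rate for either event. The most that could follow is about 5.2 enrollments, 2.6 of them to surgery, during one full review interval at planned accrual, assuming no report prompts earlier action. The likely consequence is smaller. A reader might also infer that the 20% rule is seriously weakened. It does miss these deaths, but the one-event suspension normally acts first, so that adds little.

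This should be changed because it concerns patient safety and costs little, not because oversight is lacking.

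**What to change.** With DSMB agreement, amend the list in 2.3.3, 8.2 and 8.3.5 in the same words:

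1. Add a fifth trigger: *death from any cause within 30 days of the procedure*. Using all causes removes the judgment of relatedness from the decision to pause.
2. Extend item 1 to *any intracranial hemorrhage within 30 days of the procedure*. This is cleaner than stating that stroke includes hemorrhagic stroke, which would also require amending the ischemic-only definition in 2.3.3.

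The cost is two wording changes in three places and an occasional extra pause for DSMB review. No added imaging is needed, since the change concerns events found clinically.
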